9.7.1.5 Study medication

9.7.1.5.1 Duration of treatment exposure

Duration of the treatment exposure (in days) will be summarized by using n, mean, standard deviation, minimum, Q1, median, Q3, maximum for the safety set.

The duration of the treatment exposure for a patient, regardless of temporary interruptions of usage of the study drug, is defined as

date of last study drug intake – first study drug date + 1.

The durations on each dose level, time from Visit 1 to the first dose of each dose level, and time from the first dose intake to the final top dose will also be summarized.

Duration of total exposure to study drug (excluding interruptions) will be computed as

- date of last study drug intake – first study drug date + 1 – *number of days of treatment interruption*.

The duration of total exposure to study drug will be summarized by using n, mean, standard deviation, minimum, Q1, median, Q3, maximum for the safety set.

9.7.1.5.2 Doses and Dose levels

Table 9-2 Dose and dose level

i	Dose level i	Level i dose
0	0	0 mg
1	1	50 mg
2	2	100 mg
3	3	200 mg

Average dose and dose level will be summarized by visit and overall study (n, mean, standard deviation, minimum, Q1, median, Q3, maximum).

Average dose at a given visit will be calculated as the sum of reported doses (including zero doses for interruption) / Total number of patients.

The formula for the average dose level will be calculated as the sum of reported dose levels (including dose level 0 for interruption) / Total number of patients.

The overall average (daily) dose will be calculated as:

1. Daily dose for each patient will be calculated as

$$\frac{\sum_{i=0}^3 (\text{no. of days on taking dose level } i) \times (\text{level } i \text{ dose})}{\sum_{i=0}^3 (\text{no. of days on taking dose level } i)},$$

The definitions of dose level *i* and level *i* dose are described in Table 9-1. If a patient takes two different dose levels in one day (e.g., drug titrations or discontinuations due to safety concern), then 0.5 day will be counted for the patient on both two dose levels in the day.

2. Average daily dose for each patient over patients.

For the average overall dose level, the formula is similar to that for overall average (daily) dose by using "dose level *i*". to replace "level *i* dose"

Frequency and percentage of patients at each dose level will be summarized by visit.

The last recorded treatment on the drug administration form will be presented with the number and percentage of patients on each dose level, including dose level 0.

The average dose related to the last recorded treatment will also be summarized, for both cases of including all patients in the SAF and excluding dose level 0 patients.

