5.1 Protocol requested treatment

5.1.1 Investigational treatment

All eligible patients will receive LCZ696 in addition to optimal CHF therapy, as considered appropriate by the investigator and in accordance with standard therapy guidelines, but with the exception of an ACEI or ARB as this will be replaced by LCZ696. The use of an ACEI or an ARB in addition to LCZ696 is strictly prohibited.

The Sponsor will provide the following open-label study medication in bottles:

- LCZ696 50 mg film-coated tablets (LCZ696 dose level 1)
- LCZ696 100 mg film-coated tablets (LCZ696 dose level 2)
- LCZ696 200 mg film-coated tablets (LCZ696 dose level 3)

Sufficient medication will be provided for treatment according to the study protocol, including additional medication to allow for delayed visits.

Medication labels will be in the local language and comply with the legal requirements of each country. They will include storage conditions for the drug.

The target p.o. dose of LCZ696 is 200 mg bid. For patients not tolerating the target dose, LCZ696 will be titrated down to a lower dose level twice a day, at the investigator's discretion, based on the defined safety and tolerability criteria ([Appendix 3](#), [Appendix 4](#) and [Appendix 5](#)).

For the initial treatment doses (50 or 100 mg bid) administered up to visit 2 and 3, the protocol indicates that the dose could be administered 1-to-2 weeks prior to the next visit. However, treatment should last for a **minimum of 1 week** before up-titrating to the next dose strength.

Recommended starting LCZ696 dose

For patients who tolerated **dose level 3** (either 200 mg LCZ696 bid or 10 mg enalapril bid) in the PARADIGM-HF study, the recommended starting dose is 100 mg LCZ696 bid. Similarly, for patients who maximally tolerated **dose level 2** (either 100 mg LCZ696 bid or 5 mg enalapril bid) in the PARADIGM-HF study, the recommended starting dose could be 100 mg LCZ696 bid. These patients can be up-titrated to 200 mg LCZ696 bid at a later time at the discretion of the investigator.

If, in the investigator's judgment, the patient may not tolerate the proposed starting dose of 100 mg LCZ696 bid, the patient could start with 50 mg LCZ696 bid and be up-titrated at the time of subsequent visits.

The starting dose of 50 mg bid is also recommended for patients who previously only tolerated dose level 1(either LCZ696 50 mg bid or enalapril 2.5 mg bid) in the PARADIGM-HF study.

Table 5-1 Recommended starting dose

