The patients will be instructed to take their morning study drug p.o. dose at approximately 08:00 (8:00 AM) and their evening study drug p.o. dose at approximately 19:00 (7:00 PM). The study medication should be taken with a glass of water with or without food. If the patient misses taking any study drug dose, he/she should take it as soon as possible, unless it is almost time for the following scheduled dose. In this case, the patient should skip the missed dose and return back to his/her regular study drug administration schedule.

The investigator should promote compliance by instructing the patient to take the study drug exactly as prescribed and by stating that compliance is necessary for the patient's safety and the validity of the study. The patient should be instructed to contact the investigator if he/she is unable to take the study drug as prescribed for any reason.

Visit 2 (at 1-to-2 weeks after starting LCZ696 treatment)

Study procedures will be completed, including an assessment of the patient's tolerability to LCZ696 50 mg bid (dose level 1) or LCZ696 100 mg bid (dose level 2).

IRT will be contacted and the patient dispensed bottles of LCZ696 for the target dose appropriate for each patient (depending on the dose-level tolerated in PARADIGM-HF and the judgment of the investigator). The recommended steps to up-titrate the dose are indicated below.

- For those who maximally tolerated **dose level 1** in PARADIGM-HF, additional tablets for a dose of LCZ696 50 mg bid will be dispensed at Visit 2 (if the investigator chooses not to administer a higher dose to the patient) and taken for 1-to-2 weeks before returning to the study center for Visit 3.
- For patients that maximally tolerated **dose level 2** in PARADIGM-HF, additional tablets for a dose of LCZ696 100 mg bid will be dispensed at Visit 2 (if the investigator chooses not to administer a higher dose to the patient) and taken for 1-to-2 weeks before returning to the study center for Visit 3.
 - However, if a patient tolerated dose level 3 in PARADIGM-HF, they will receive additional tablets for a dose of LCZ696 200 mg bid, which will be taken for 1-to-2 weeks before returning to the study center for Visit 3.
- Any patient at dose level 1 or 2 can be up-titrated to a higher dose of LCZ696 at Visit 2 or any time thereafter at the discretion of the investigator.

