LCZ696 tablets should be taken p.o. in the morning at approximately 08:00 (8:00 AM) and again in the evening at approximately 19:00 (7:00 PM). The instructions provided at Visit 1 for taking the tablets and compliance should again be reviewed with each patient.

Visit 3 (at 2-to-4 weeks), Visit 4 (at 3 months), Visit 5 (at 6 months), Visit 6 (at 12 months), Visit 7 (at 18 months) and Visit 8 (at 24 months)

Study procedures will be completed before contacting the IRT to dispensed bottles of LCZ696 50 mg, 100 mg or 200 mg tablets to patients. The instructions provided at Visits 1 and 2 for taking the tablets and compliance should again be reviewed with each patient.

Visit 9 (at 30 months)

Study procedures will be completed before contacting the IRT to record the patient's attendance for this visit but not to dispense study drug.

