If down-titration is necessary, the patient should be down-titrated to the next lower dose level (Table 5-2 below). The patient may continue to receive the lower dose level for a recommended period of 1 to 4 weeks, or longer based on the investigator's judgment, before re-challenging the patient with the next higher dose level. For example, a patient who encounters tolerability problems at the target dose of 200 mg LCZ696 bid (dose level 3), should receive the study drug at dose of 100 mg LCZ696 bid (dose level 2) for 1 to 4 weeks. Then, based on the investigator's judgment, he/she should be re-challenged with up-titration back to dose level 3.

Table 5-2 LCZ696 dispensed during the open-label treatment period

Study visit	Dose level	LCZ696
Dispensed at Visit 2 and all subsequent visits	3 ^a	200 mg bid
Dispensed at Visit 1 and available for any visit after Visit 1	2 ^b	100 mg bid
Dispensed at Visit 1 for patients that tolerated only dose level 1 in PARADIGM and available for any visit after Visit 1	1 ^c	50 mg bid

a. This dose level should be maintained for as long a duration as possible. If down-titration is necessary due to side effects, the patient should be re-challenged as soon as medically possible per the investigator's judgment.

b. Only if dose level 3 is not tolerated despite modification of other non-disease-modifying HF medications.

c. Only if dose levels 2 and 3 are not tolerated despite modification of other non-disease-modifying HF medications.

If the tolerability issues are not alleviated despite down-titration by one dose level, the investigator may lower the study drug dose further to the next lower level for 1 to 4 weeks, up to temporary or permanent withdrawal of the study drug. Again, once stable, the patient should be re-challenged with up-titration to the next higher dose level every 1 to 4 weeks in an attempt to bring back the patient gradually to the target study drug dose level (dose level 3).

The investigator may choose the next dose level for down- or up-titration according to his or her judgment (Table 5-2). As discussed in [Section 5.5.5](#), the IRT should be contacted to register any changes in the patient's LCZ696 dose level, including cases of temporary and permanent withdrawal of the study drug, and to obtain the medication numbers of the LCZ696 supplies required for the new dose level.

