9.7.1.5.3 Treatment exposure in subgroups

The above treatment exposure analyses will be repeated for the following subgroups:

- Age group <65, ≥65 years
- Age group <75, ≥75 years

- Gender (male, female)
- Race (Caucasian, Black, Asian, Other)

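### The SAP's average daily dose counts only one of the two daily intakes, so it shows about half the milligrams taken per day

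*SAP*

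**What the plan says.** SAP 9.7.1.5.2 first assigns an amount to each level in "Table 9-2 Dose and dose level": 0 mg for level 0, 50 mg for level 1, 100 mg for level 2 and 200 mg for level 3. It then describes the overall summary: "The overall average (daily) dose will be calculated as". The first step is per patient: "Daily dose for each patient will be calculated as" the sum of days on each level times that level's amount, divided by the sum of days on all levels. The second step averages these values over patients. A day with two different levels counts as half a day on each.

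SAP 9.7.1.5.3 carries the statistic into age, sex and race groups: "The above treatment exposure analyses will be repeated for the following subgroups".

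The protocol doses every active level twice a day:

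- Section 5.1.1: "The target p.o. dose of LCZ696 is 200 mg bid". The same section lists 50, 100 and 200 mg tablets as dose levels 1, 2 and 3.
- Section 5.5.4, Visit 2, names the lower levels as "LCZ696 50 mg bid (dose level 1) or LCZ696 100 mg bid (dose level 2").
- Section 5.5.4 also gives the timing: "LCZ696 tablets should be taken p.o. in the morning at approximately 08:00 (8:00 AM) and again in the evening".
- Section 5.5.5, on stepping down from target, says the patient "should receive the study drug at dose of 100 mg LCZ696 bid (dose level 2").

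**The concern.** The amounts in Table 9-2 are the size of one intake. A day-weighted mean of them is the average size of an intake, not the amount taken in a day, yet the SAP labels it daily both for each patient and overall. Neither the table nor the formula mentions bid, mg/day or a doubling.

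Safety and tolerability are the trial's only objective, and Protocol 5.5.5 asks investigators to try to keep patients at 200 mg bid. How much drug patients actually took is therefore a basic tolerability descriptor. A reader who takes the label at its word would halve the figure to recover the bid dose and conclude that patients sat near level 2, while the average dose level reported in the same section would put them near level 3.

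**Working it through.** The SAP states no numerical value for this statistic, so there is no published figure to reproduce. The check applies the SAP formula as written and then repeats it with the milligrams taken per day.

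**Inputs.** Amounts per level come from SAP Table 9-2. Two intakes per day come from Protocol 5.1.1 and 5.5.4.

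| Dose level | Table 9-2 amount (mg) | Intakes per day | mg per day |
|---|---|---|---|
| 0 | 0 | none | 0 |
| 1 | 50 | 2 | 100 |
| 2 | 100 | 2 | 200 |
| 3 | 200 | 2 | 400 |

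**Formula.** Patient value = Σ(days on level i × amount for level i) / Σ(days on level i), for i = 0 to 3. Doubling every weight doubles the result, so on full dosing days the ratio is exactly 2 whatever the dosing history.

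**One patient (assumed history).** 10 days interrupted, 14 days on level 2 and 890 days on level 3, total 914 days.

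- SAP weights: (14 × 100 + 890 × 200) / 914 = 179400 / 914 = 196.3 mg.
- Daily amounts: (14 × 200 + 890 × 400) / 914 = 358800 / 914 = 392.6 mg/day.
- Average dose level: (14 × 2 + 890 × 3) / 914 = 2698 / 914 = 2.95.
- Reading 196.3 as mg/day on a bid regimen gives 196.3 / 2 = about 98 mg bid, close to level 2.

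**Across a range of person-time mixes (assumed).**

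| % of person-time at levels 0/1/2/3 | SAP formula (mg) | mg per day |
|---|---|---|
| 0/5/10/85 | 182.5 | 365 |
| 0/10/15/75 | 170 | 340 |
| 5/15/20/60 | 147.5 | 295 |

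**Does the half-day rule correct this?** No. A day with 100 mg in the morning and 200 mg in the evening scores 0.5 × 100 + 0.5 × 200 = 150, against 100 + 200 = 300 mg taken. The rule splits the day properly under either set of weights; it does not add the two intakes.

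**Single-intake first and last days.** These are the only departure from a ratio of 2.

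- In the 914-day example, removing one 100 mg intake on the first day and one 200 mg intake on the last gives (358800 − 300) / 914 = 392.2 mg/day, a ratio of 1.998.
- For 14 days at 100 mg bid, (2800 − 200) / 14 = 185.7 mg/day against 100 mg by the SAP formula, a ratio of 1.86.

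The SAP figure is thus about half the daily amount, and closer to exactly half the longer the exposure.

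**The case against.** The strongest reply is that this is a unit label, not bad arithmetic. As a mean amount per intake the formula is correct, and the half-day rule fits that reading. The overall, by-visit and last-recorded averages all run on the same 0 to 200 mg scale, keyed by Table 9-2. On that key, 196.3 mg and level 2.95 agree. The protocol always names doses as 50, 100 or 200 mg bid and never as a daily total, so many readers would compare 196 with 200 and reach the right answer. The word daily might even have been meant to separate a day-weighted average from the by-visit one. Protocol 9.3 plans only duration of exposure, so average dose is an extra descriptive summary. Finally, the heart failure harmonization plan cited in SAP 9.7.1 is not available here and could contain a conversion.

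Much of this limits the consequence, and that stands: a reader used to the mg bid convention may not be misled, and the two summaries conflict only if the label is believed. It does not remove the error. Calling the per-patient quantity a daily dose leaves little room for the day-weighted reading. The SAP sets out its own formula and weights for this calculation without deferring to the harmonization plan, so an unseen conversion cannot be assumed to override them.

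**Conclusion.** The concern holds. Followed as written, SAP 9.7.1.5.2 reports under a daily label a figure that is half the milligrams taken per day, apart from small edge effects in very short exposures. The factor rests only on twice-daily dosing and the Table 9-2 amounts; the day counts and person-time mixes above are assumed for illustration.

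The scope is narrow: the overall average daily dose and its subgroup repeats. Durations, average dose level and percentages at each level are right as planned, and no adverse event or vital-sign analysis uses the figure. The by-visit and last-recorded average doses share the scale but are not called daily, so they lack only a unit.

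Confidence is high that the written formula and its label disagree. It is moderate that the report would print the figure uncorrected, because the harmonization plan cannot be seen. It should be fixed, but no safety conclusion depends on it.

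**What to change.** Choose one of two repairs in SAP 9.7.1.5.2:

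- **Relabel.** Keep the present weights, delete the word daily and call the result average dose per administration (mg bid). This is the simpler repair and keeps all average doses in the section on one scale.
- **Reweight.** Add a total-daily-dose column to Table 9-2 (0, 100, 200 and 400 mg/day) and use it in the daily-dose formula. The section then has two scales, which makes explicit units essential.

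Under either repair, state the unit (mg per administration or mg/day) on the by-visit and last-recorded average doses. Carry the change into the subgroup tables of 9.7.1.5.3. Also correct a clerical slip: the text under the formula sends the reader for the dose definitions to Table 9-1, which holds the analysis-set exclusion rules, when they are in Table 9-2.

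The cost is a few words in the SAP and one label or one set of weights in the exposure program. It needs no new data and leaves patient dosing unchanged.

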9.7.1.5.3 Treatment exposure in subgroups

The above treatment exposure analyses will be repeated for the following subgroups:

- Age group <65, ≥65 years
- Age group <75, ≥75 years

- Gender (male, female)
- Race (Caucasian, Black, Asian, Other)

9.7.1.5.4 Concomitant heart failure medications

Concomitant heart failure medications are defined as any HF medications administered after the enrollment date into the study. Concomitant HF medications will be summarized by ATC and preferred term using frequency tables for the safety set.

9.7.1.6 Analysis of the primary variable

The primary objective of this study is to evaluate the safety and tolerability of LCZ696 and to provide heart failure patients from PARADIGM-HF with open-label access to this investigational drug. The safety evaluation will include:

- Adverse events
- Vital signs

9.7.1.6.1 Adverse events

Any adverse events (AEs) occurred during the study period will be assessed, overall, by primary system organ class, by preferred term, by maximum severity, by relationship to the investigational drug according to the Medical Dictionary for Regulatory Activities (MedDRA).

The MedDRA version used for reporting the study will be described in a footnote.

Within each AE report, the following rules are applicable. If a subject reported more than one adverse events with the same preferred term, the adverse event with the greatest severity will be presented. If a subject reported more than one adverse event within the same primary system organ class, the subject will be counted only once with the greatest severity at the system organ class level, where applicable.

The number and percentage of subjects reporting the following AEs will be summarized by primary system organ class, preferred term.

- Overall AEs
- Serious adverse events (SAEs)
- AE of special interests (AESIs), i.e. AEs of hypotension, hyperkalemia or renal dysfunction
- Angioedema/angioedema-like events
- Deaths
- AEs leading to study drug dose adjustment/temporary interruption or permanent discontinuation
- AEs leading to study drug permanent discontinuation including deaths
- AESIs leading to study drug permanent discontinuation with patients starting rescue medication(s) (ACEI/ARB)

The most common adverse events reported ($\geq 1\%$ for each preferred term in the SOC-PT table) will be presented in descending frequency according to its incidence starting from the most common event.

For the legal requirements of ClinicalTrials.gov and EudraCT, two required tables on treatment emergent adverse events which are not serious adverse events with an incidence greater than 5% and on treatment emergent serious adverse events and SAE suspected to be related to study treatment will be provided by system organ class and preferred term on the safety set population.

If for a same patient, several consecutive AEs (irrespective of study treatment causality, seriousness and severity) occurred with the same SOC and PT:

- a single occurrence will be counted if there is ≤ 1 day gap between the end date of the preceding AE and the start date of the consecutive AE
- more than one occurrence will be counted if there is > 1 day gap between the end date of the preceding AE and the start date of the consecutive AE

For occurrence, the presence of at least one SAE / SAE suspected to be related to study treatment / non SAE has to be checked in a block e.g., among AE's in a ≤ 1 day gap block, if at least one SAE is occurring, then one occurrence is calculated for that SAE.

The number of deaths resulting from SAEs suspected to be related to study treatment and SAEs irrespective

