3.3 Rationale of dose/regimen, route of administration and duration of treatment

Based on safety data from the PARADIGM-HF single-blind, sequential design run-in period, LCZ696 was well-tolerated, with over 90% of patients achieving the target dose.

A strong rationale exists for the target dose of LCZ696 in HF-rEF patients. A p.o. dose of LCZ696 200 mg bid delivers similar exposures of valsartan (assessed by AUC) as Diovan® 160 mg bid, the highest approved Diovan® dose for HF and the dose recommended in international guidelines for the treatment of HF. In addition, biomarker analysis (increase in ANP and cGMP) indicates that this dose delivers approximately 90% of its maximal NEP inhibition.

Most importantly, this study will target the oral dosing regimen for LCZ696 identical to that which showed a mortality and HF hospitalization benefit superior to that of enalapril in PARADIGM-HF.

[*] The study will continue in an individual country for a minimum of 12 months and until a marketing authorization has been received and the drug product becomes commercially available in that country (which is expected to be up to 30 months) from the date of the first eligible patient enrolled in that country, or until the study is terminated, whichever comes first. Within the study period, the duration of treatment for an individual patient will be at the discretion of the investigator.

[* For **Denmark only**, the above paragraph will read as follows:

From the date of the first eligible patient enrolled in Denmark, the study will have a duration of 12 months. The treatment duration may be re-evaluated and an amendment issued to adjust the treatment duration.]

[* For the **United Kingdom only** the above paragraph will read as follows:

From the date of the first eligible patient enrolled in the UK, the study has a minimum duration of 12 months and a maximum duration of 20 months. The treatment duration may be re-evaluated and an amendment issued to adjust the treatment duration].

[* For **Germany only**, the above paragraph will read as follows:

From the date of the first eligible patient enrolled in Germany, the study will have a maximum duration of 24 months. The treatment duration may be re-evaluated and an amendment issued to adjust the treatment duration.]

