9.4 Analysis of the primary variable(s)

The primary objective of this study is to evaluate the safety and tolerability of LCZ696 and to provide heart failure patients from PARADIGM-HF receiving open-label investigational drug. The primary assessment for safety will be based on the frequency of adverse events (AE) including:

- Overall AEs
- Serious adverse events (SAEs)
- adverse events of special interest (AESI), i.e., hypotension, hyperkalemia, or renal dysfunction
- Angioedema/angioedema-like events
- Deaths

- AEs leading to study drug dose adjustment/temporary interruption or permanent discontinuation
- AEs leading to study drug permanent discontinuation, including deaths
- AESIs leading to study drug permanent discontinuation with patients starting rescue medication(s) (ACEI/ARB)

AEs will be summarized as appropriate by presenting the number and percentage of patients reporting AEs by primary system organ class, by preferred term, by maximum severity, and by relationship to the investigational treatment.

In addition, the primary assessment for safety is the reporting of vital signs (i.e., sitting systolic blood pressure, sitting diastolic blood pressure, and heart rate) by visit with standard summary statistics (n, mean, standard deviation, minimum, Q1, median, Q3, maximum), including changes from baseline.

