9.5.3 Statistical model, hypothesis, and method of analysis

The number and frequency of adverse events will be summarized by primary system organ class, and preferred term. Serious adverse events and adverse events of special interest will be summarized in Clinical narratives.

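### In the text available, the eight primary AE categories are reported only as n (%) over an undefined period while follow-up varies, so the percentages have no time horizon

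*SAP*

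**What the plan says.** **Measure.** Protocol 9.4 makes AE frequency the first-named primary safety assessment and states: "AEs will be summarized as appropriate by presenting the number and percentage of patients reporting AEs by primary system organ class". SAP 9.7.1.6.1 repeats the same eight categories: "The number and percentage of subjects reporting the following AEs will be summarized by primary system organ class, preferred term". Protocol 9.5.3 adds that "Serious adverse events and adverse events of special interest will be summarized in Clinical narratives". The registry tables in SAP 9.7.1.6.1 count occurrences under a one-day-gap rule, again without a time denominator.

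**Window.** The SAP's wording is "Any adverse events (AEs) occurred during the study period will be assessed, overall, by primary system organ class"; it gives that period no start, end or length.

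**Follow-up (protocol 3.3).**
- Denmark: "From the date of the first eligible patient enrolled in Denmark, the study will have a duration of 12 months".
- UK: "the study has a minimum duration of 12 months and a maximum duration of 20 months".
- Germany: "the study will have a maximum duration of 24 months".
- Elsewhere: a minimum of 12 months, ending at local availability, "which is expected to be up to 30 months) from the date of the first eligible patient enrolled in that country".

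The first three may be changed by amendment. Within these limits, treatment length is at the investigator's discretion. Under protocol 5.5.9, permanent discontinuation is withdrawal from the study, with a final visit and follow-up only of AEs that have already occurred. AEs are recorded from consent (protocol 7.1), and SAEs are reported to 30 days after the last dose (protocol 7.2.2).

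**Related tables.** SAP 9.7.1.5.1 summarises exposure from first to last dose, and 9.7.1.5.3 repeats this by age, sex and race. SAP 9.7.1.8 repeats the AE analysis in the same subgroups. No passage links exposure to the AE counts.

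**The concern.** A percentage of patients with an event is a risk only once the time over which it accrued is stated. Here that time differs between countries. Because each country's clock starts at its first patient, it also differs between early and late entrants within a country, and it is cut short by discontinuation. Two things follow. The pooled figure depends on country mix and entry dates as well as on the drug's safety, and so do the SAP's 1% and 5% cut-offs for listing common events. And in the 9.7.1.8 subgroups, two groups at the same risk could show different percentages if their follow-up differed. Describing safety is the whole primary objective, so what is at stake is whether that description can be read or set beside other data.

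**Working it through.** **1. What the plan supplies.** The documents give no AE rate, dropout rate, enrolment span or country mix. The one related figure is planned enrolment: 5,000/8,436 = 59.3%, which matches the stated 59%; nothing below depends on it. Every rate and follow-up share below is an assumption.

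**2. Dependence on follow-up.** With constant rate λ per year, F(m) = 1 − exp(−λm/12). A 12-month risk of 10% means λ = −ln(0.90) = 0.105. Then F(12) = 10.0%, F(20) = 16.1%, F(24) = 19.0%, F(30) = 23.2%. If 75%, 50% or 25% of patients have 12 months and the rest 30, the pooled figure is 13.3%, 16.6% or 19.9%. For entry date: with an assumed 6-month enrolment span in a country closing at 12 months, the last entrant has 6 months and a 5.1% risk, and the average over uniform entry is 7.6%.

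**3. Subgroups at equal risk.** Let a share s have 30 months and the rest 12, so that the percentage is s·F(30) + (1−s)·F(12). Ratios for two subgroups with different s:

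| Assumed rate per year | F(12) | F(30) | s 45% v 55% | s 40% v 60% | s 25% v 75% |
|---|---|---|---|---|---|
| 0.05 | 4.88% | 11.75% | 1.086 | 7.6 v 9.0%: 1.180 | 1.521 |
| 0.20 | 18.13% | 39.35% | 1.077 | 26.6 v 30.9%: 1.159 | 1.453 |
| 1.0 | 63.21% | 91.79% | – | 74.6 v 80.4%: 1.08 | – |
| 2.0 | 86.47% | 99.33% | – | 91.6 v 94.2%: 1.03 | – |
| 0.40 in months 0–3, then 0.012 | 10.33% | 11.93% | – | 11.0 v 11.3%: 1.029 | 1.075 |

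In the moderate mixes (45/55 and 40/60) the distortion is about 1.03- to 1.2-fold. The 25/75 mix is an extreme.

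**4. Why a rate alone is not enough.** In the early-cluster row, mean time at risk to first event is 0.913 years over 12 months and 2.247 years over 30. At s = 0.40 the rate is 0.1097/(0.4×2.247 + 0.6×0.913) = 7.58 per 100 patient-years. At s = 0.60 it is 0.1129/(0.6×2.247 + 0.4×0.913) = 6.59. The rates differ at equal risk, while 12-month cumulative incidence is 10.3% in both groups.

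**5. Can a reader use the exposure tables instead?** The crude rate is 100·[s·F(30) + (1−s)·F(12)]/[2.5s + (1−s)].
- λ = 0.05: 7.63/1.6 = 4.77 and 9.00/1.9 = 4.74, against a true 5.0 (about 5% low).
- λ = 0.20: 26.61/1.6 = 16.63 and 30.86/1.9 = 16.24, against a true 20 (17% and 19% low).

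The shortfall arises because exposure keeps accruing after the first event.

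**6. Choice of window.** A 30-day tail after the last dose is 30/(365+30) = 7.6% of the window after 12 months of treatment, 30/(913+30) = 3.2% after 30 months, and 30/(91+30) = 25% after 3 months. SAEs are collected in that tail. Non-serious AEs are not routinely collected after the final visit, and events defined by a dosing action cannot occur in it. One common window would therefore dilute those categories, most of all in early stoppers.

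**The case against.** The case for leaving the plan alone is considerable. The study has one arm and plans no treatment comparison (SAP 9.7.3). The SAP carries out what protocol 9.4 specified. Exposure is shown overall and in the very subgroups used for AEs, so a reader would see an imbalance. For high-frequency categories such as overall AEs, or for events clustered in up-titration, the distortion is small (1.03 to 1.08 in the 40/60 mix), and in the early-cluster case a person-time rate misleads more than the percentage does.

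Most of this stands. It limits the point to interpretation, and it is why 12-month cumulative incidence is needed beside the rate. It does not supply the missing time horizon: showing an imbalance does not correct for it, and first-to-last-dose exposure is not time at risk to first event.

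Three stronger readings are tempting but unsupported:
- **That no time-adjusted AE estimate is planned anywhere.** SAP 9.7.1 refers to a heart-failure harmonisation MAP that is not among the documents, and the AE section breaks off in mid-sentence in the text available. The absence holds only for what can be read.
- **That the subgroup percentages will be biased.** Nothing shows follow-up differing by age, sex or race, and country, where it does differ, is not a planned subgroup.
- **That the full 12-versus-30-month contrast** (10.0% v 23.2%) measures the error in a planned table. No planned table compares those two lengths.

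**Conclusion.** The point holds as one of interpretation. In the available text the eight primary AE categories are reported only as n (%) over an undefined period, while country follow-up runs from 12 to about 30 months and individual follow-up also depends on entry date and discontinuation. The variation in follow-up is built into the protocol. Shorter follow-up for later entrants is inferred from the country clock starting at the first patient.

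The size is illustrative: it rests on assumed rates, on a two-point mix of 12 and 30 months and, apart from the early-cluster case, on constant hazards. A reader might infer that the primary results would be invalid. They would not be: the counts and percentages remain correct descriptions of what was recorded, and no error rate or power is involved. This is a cheap improvement that should be made.

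**What to change.** Keep n (%). In SAP 9.7.1.6.1, for each of the eight categories at category level only (not each SOC or preferred-term row), overall and preferably in the 9.7.1.8 subgroups, add:
1. patients with a first event per 100 patient-years at risk, with 95% CI;
2. cumulative incidence at 12 months, with 95% CI, treating death as a competing event where it is not itself the event.

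Define the window and count events and person-time over the same window:
- **SAEs and deaths:** first dose to last dose + 30 days, or death if earlier.
- **Overall AEs, AESIs, angioedema and the three dosing-action categories:** first dose to last dose, with later SAEs footnoted.

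For the dosing-action categories (adjustment, interruption or discontinuation; permanent discontinuation; AESI discontinuation with rescue), use AE onset as the event date, including where rescue is required. Treat permanent discontinuation for another reason as competing, and state whether a death after stopping for another reason counts. Footnote AEs before first dose, and state that censoring at discontinuation may be informative.

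If the harmonisation MAP already specifies such estimates, a reference to it in 9.7.1.6.1, with the window, is enough.

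**Cost.** SAP wording and modest programming. AE and dosing dates are already collected, but time at risk to first event must be derived. With all subgroups the output is 8 × (1 + 2 + 2 + 2 + 4) = 88 rows; overall only, it is 8. Imputed dates add some imprecision: the 1 July rule can be up to 183 days off, though SAP 9.7.1.4.1(d) allows better information to be used. Intervals in small subgroups will be wide.
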